## **16.5** Appendix 5 - Protocol Amendments

This is the seventh version of the protocol. To date, there have been six protocol amendments. Details of the key changes made in each version are provided in the table below.

Protocol version	Effective date	Section	Change	
1.0	24 th Aug 2018	All	No change - new protocol	
2.0	14 th Nov	FDA requested char	nges	
	2018	Section 1.6.2	Start of corticosteroid therapy was clarified	
		Section 4.2	Clarification of terminology "standard therapy" and protocol in and exclusion criteria (#4)	
			Clarification if patients will be enrolled who are eligible to receive therapies with known clinical benefit	
		Section 5.5	Update DLT criteria	
		Section 3.3	Define pre-specified stopping rules to pause enrolment	
		Section 5	Revise protocol to align management of toxicities according to Appendix 1 and Table 5-5 of protocol	
		Section 5	Table 5-2 revised for administration sets	
		Section 6	Addition of antiacetyl-choline receptor (AChR) autoantibodies to autoantibody panel	
		IRB requested chan	ges	
		Section 3.1.2	Consistency of description of antitumor activity	
		Section 9.2	Consistency of number of patients enrolled throughout the entire study	
		Section 4.2	Change age of participants to $\geq 18$ years for all countries (excluding Taiwan)	
		Kymab internal changes		
			Various changes for correction of typographical errors and clarifications	
3.0	24 th Jan	MHRA requested cl	hanges	
	2019	Section 5.2.3	The observation period of the sentinel patient in the combination cohort 1 of KY1044 with atezolizumab has been prolonged to 72 hours instead of 48 hours.	
		Section 3.3	Specific wording has been added to clarify the detailed communication process, in the event that the study needs to be put on hold	
		Section 5.7	Table 5-6 has been updated to clarify the duration for when and how long, life attenuated vaccines are prohibited	
		Protocol synopsis Section 4.2 Section 5.8	The duration required for contraception of females and males (barrier contraception) have been changed to at least 5 months after discontinuing study treatment, or longer if the half-life of KY1044 is observed to exceed that of atezolizumab.	

Protocol version	Effective date	Section	Change
		Kymab internal cha	nges
		Section 4.1.1	The number of patients required in each cohort in Phase 1 has been clarified
		Section 5.4.2	Table 5-2 has been updated and corrected for dose level -1
		Section 5.4.4	The requirements for the assessment of DLT data based on three patients has been clarified
		Section 6	Table 6-8 has been amended according to the changes in the Lab manual
			Table 6-1 and Table 6-2 have been amended according to changes in Table 6-8
			Section 6.5.8 has been amended to specify Troponin I according to changes in the laboratory manual
4.0	08 May	Section 1.4.3.1	Updated date relating to atezolizumab approvals.
	2019	Section 4.3	Updated to clarify the requirements for use of anticoagulant treatment.
		Section 5.6.3	Updated as Appendix 5 atezolizumab guidance for investigators removed.
		Section 6	Section 6.5.6 revised to enable use of local labs if necessary
		Appendix 3	Updated list of atezolizumab adverse events of special interest.
		Appendix 5	Atezolizumab guidance for investigators removed.
5.0	28 Jul 2020	Protocol Synopsis: Study design; Protocol Synopsis: Study population; Sections 1.5.2; 3.1; 3.1.2; 3.1.4; 5.2.1; 5.9; 9.2	The study design for Phase 2 has been changed to introduce an initial Phase 2 dose assessment part in one or more specific indication(s) to compare the efficacy and biomarker readouts of two biologically relevant dose levels of KY1044 (as single agent or in combination with atezolizumab) in a more homogeneous patient population.
		Protocol Synopsis: Sample size; Sections 1.5.2; 3.1.3; 4.1; 9.2	The number of patients in Phase 1 has been increased from 112 to approximately 150. The number of patients in Phase 2 has been decreased from a maximum of 300 to a maximum of 262.
		Protocol Synopsis: Study population; Protocol synopsis: Key inclusion criteria; Sections 1.5.2; 3.1.4; 4.2; 5.4.7	Clarification that patients will be treated with KY1044 as single agent in Phase 2 only if evidence of anti-tumor activity is detected in the dose escalation/enrichment Phase 1 parts.
		Protocol Synopsis: Key exclusion criteria; Section 4.3	Update to Exclusion criterion 5 in the Protocol Synopsis and Exclusion criterion 6 in Section 4.3 to exclude patients with any severe infection within 4 weeks of initiation of study treatment to align with the atezolizumab required exclusion criteria.

Protocol version	Effective date	Section	Change
		Protocol Synopsis: Statistical analysis; Protocol Section 9.4	Text was updated to account for multiple dose groups and schedules. It was clarified that Phase 2 will be reported by dose group(s) in addition to indication.
		Section 1.6.5	Addition of benefit/risk of KY1044 as single agent and in combination with atezolizumab regarding potential infections with SARS-Cov-2.
		Section 3.1.4	Amendments have been made to the study design figure to include the total patients in Phase 1 and Phase 2, to clarify that approximately 36 patients will be enrolled in the Phase 1 dose escalation part (KY1044 monotherapy and in combination with atezolizumab), and to increase the number of patients in the enrichment pool from 40 to approximately 78. An initial Phase 2 dose assessment part has been added, and it has been clarified that patients will be treated with KY1044 as a single agent in Phase 2 only if evidence of anti-tumor activity is observed in the Phase 1 dose escalation/enrichment parts. A footnote has been added to clarify that, for the tumor types selected for Phase 2, the number of patients enrolled per group could be reduced, depending on enrolment feasibility in the ongoing study.
		Section 3.3; 5.4.4	It was clarified that, in addition to continuing until identification of the MTD and/or the RP2D, dose escalation may also continue until completion of all defined dose levels, or a decision that further increase of dose is not warranted.
		Section 5.2.2	The infusion schedule has been updated so that, when given in combination, both IMPs are to be administered within 24 hours.
		Section 5.2.4	A sentence has been added to clarify that if an infusion reaction is caused by KY1044, the atezolizumab infusion may be delayed until the next day and/or until recovery from the event.
		Section 5.6.1	Active SARS-Cov-2 infections should be treated as AEs, as should any other concurrent illnesses, and treatment interruption should be considered on an individual patient basis.
		Section 5.6.3; Appendix 3	In alignment with Addendum 2 of the atezolizumab IB Version 15, "Systemic immune activation" has been amended to 'immune-mediated reactions'.
		Section 6	The atezolizumab PK sampling schedule was clarified in Table 6-1 for Phase 1 and Table 6-2 for Phase 2.
		Section 6.3.1	Safety analysis has been added to the alternative biomarkers to be able to explore biomarkers for infusion reactions. Blood volumes for PBMCs for pharmacogenomic testing, immunoprofiling and receptor occupancy have been clarified in Table 6-4.
		Section 6.4.2	A sentence has been added to allow PK samples to be used for analysis of alternative biomarkers of safety and efficacy. The PK sampling timetable has been clarified in Table 6-5.

Amended Clinical Trial Protocol 07
KY1044/SAR445256-KY1044-CT01/TCD17370 - alomfilimab

Protocol version	Effective date	Section	Change
		Section 6.5.8	The electrocardiogram collection plan timetable has been clarified in Table 6-9.
		Addendum 1	A finalized addendum dated 21 April 2020 summarizing potential adjustments for protocol visits and assessments due to circumstances created by the COVID-19 pandemic has been incorporated into the protocol.
6.0	07 May 2021	Protocol Synopsis: Study design; Protocol Synopsis: Duration of the Study; Sections 3.1, 3.2, 3.4, 3.6, 5.3, 6, 6.2.1, 6.5.6, 8.1, 8.2.2, 8.2.3	The study has been amended to allow study treatment beyond 24 months up to 48 months for patients that are deriving clinical benefit without safety concerns. The requirements for survival follow-up have been updated accordingly.
		Protocol Synopsis: Key exclusion criteria; Sections 4.3, 5.7, 6, 6.1.5, 7.1	The study design has been updated with respect to the management of SARS-CoV-2 vaccination in subjects participating in non-COVID-19 clinical trials.
7.0	10 Nov 2021	See Section Protocol	Amendment Summary of Changes

10-Nov-2021 Version number: 1

## 17 ADDENDA

## 17.1 Addendum 1

This addendum is applicable only where national/local restrictions due to COVID-19 are implemented and may therefore be in force at variable times and in certain sites only.

10-Nov-2021 Version number: 1

kymab

21 April 2020

KY1044-CT01

A Phase 1/2, open-label, multi-center study of the safety and efficacy of KY1044 as single agent and in combination with anti-PD-L1 (atezolizumab) in adult patients with selected advanced malignancies

## SUMMARY

This document is an addendum to the existing protocol KY1044-CT01, summarizing potential adjustments for protocol visits and assessments due to circumstances created by the current COVID-19 pandemic.

Recruitment to the study is being reviewed continuously to allow detailed assessments of the impact of the COVID-19 pandemic per country and site. Visits of patients and study monitors to hospitals have been restricted in most countries due to requirements for social distancing and also travel restrictions related to the COVID-19 pandemic. Additionally, scheduling of study visits and assessments may be impacted by the lack of, or availability of, study staff. The impact of COVID-19 differs at different sites, depending on the situation in each country, patient recruitment and internal site-specific procedures. These circumstances necessitate the set-up of new procedures to ensure that study oversight by the sponsor and the CRO can still be maintained.

The expectation is that the full protocol must be followed at each site wherever possible. New patients will not be started on the study unless there is an expectation that all protocol required assessments can be performed. However, for study assessments for ongoing patients at sites where restrictions due to COVID-19 are implemented, the absolute minimum requirements for safety, pharmacokinetic (PK) and biomarker analysis to allow collection of essential data on safety, drug exposure and biological activity, are summarized in this addendum.

This addendum is therefore relevant to the following sections of the protocol:

- Section 6.3 Assessment of Pharmacodynamics
- Section 6.4 Pharmacokinetic and Anti-drug Antibody Procedures
- Section 6.5.6 Safety Laboratory Tests
- Section 7 Safety Monitoring and Reporting
- Section 7.2 Important Medical Procedures to be Followed.

ADDENDUM VERSION 1.0

CONFIDENTIAL

PAGE 2
## kymab 21 April 2020 KY1044-CT01

### For study assessments for ongoing patients at sites with restrictions due to COVID-19:

### Protocol section 6.3 Assessment of Pharmacodynamics

All efforts should be made to collect all samples as per protocol, however, if this is not possible:

- Blood biomarker samples (protocol section 6.3.3 and table 6-4) C1D2 samples may be taken at C1D1 at the latest timepoint possible (6-8h after dosing together with the PK sample). C1D8 samples can be taken together with the safety assessments as per safety samples section below
- Tumor biopsies (protocol section 6.3.2) (as per protocol to be taken on C2D8) can be scheduled together with the safety assessment as described below
  - If this is not possible, then the biopsy may be taken at the next subsequent opportunity around 8 days after the last infusion, as an unscheduled biopsy

### Protocol section 6.4 Pharmacokinetic and Anti-drug Antibody Procedures

### **6.4.1 Pharmacokinetic Procedures:**

For patients who cannot attend the scheduled PK follow-up visits (C1D2, C1D8, C1D11, C1D15, C3D8, C3D11, C3D15) PK sampling at those time points may be omitted, although every effort should be made to collect C1D8 samples together with the safety assessments as per safety samples section below

- If, following removal of any restrictions due to the COVID-19 pandemic, patients remain on treatment and are ongoing in the study, any missed PK samples should be taken during later cycles, after discussion with the medical monitor/SRMO
- PK sample tubes from the unscheduled visit kits should be used for collection of these samples

#### **Protocol section 6.5.6 Safety Laboratory Tests (Table 6-8)**

Minimum requirements for safety analysis

- Safety blood samples should be collected prior to dosing (approximately every 3 weeks at every cycle) as per protocol
- Collection of follow-up blood safety samples may be reduced to once in each of Cycle 1 and Cycle 2 (approximately in the middle of the cycle between D3 and D19). The C1D8/C2D8 samples should be collected at this visit.. The C3D8 samples may be omitted or performed when the patient comes into the clinic for restaging scans (RECIST assessment).

If due to COVID-19 related issues, it is not possible to collect this minimum set of safety samples, the Kymab SRMO or PRA Medical Director will discuss the situation with the Principal Investigator and assess if the situation can be improved or if discontinuation of the dosing will need to be considered.

ADDENDUM VERSION 1.0

CONFIDENTIAL

PAGE 3

# kymab 21 April 2020 KY1044-CT01

- If the full safety analyses per table 6-8 of the protocol cannot be collected, the following analyses are an absolute minimum requirement:
  - Haematology: WBC with differential, HgB, platelets
  - Biochemistry: (AST, ALT, bilirubin, glucose, sodium, potassium, creatinine, amylase or lipase)
  - Coagulation: aPTT, PT
- In exceptional COVID-19 related circumstances section 6.5.6 of the protocol is extended to allow the use of local laboratory results for all assessment timepoints where central labs absolutely cannot be collected. Local laboratory results must be entered into the EDC as soon as possible and not later than 2 weeks after the date of the sample. Exceptionally, if entry cannot be performed within 2 weeks, anonymized reports must be sent to the PRA medical monitor for oversight purposes.

### Protocol section 7 Safety Monitoring and Reporting

Minimum requirements for safety reporting

- AE review in accordance with section 7 of the protocol must be performed at least once per cycle
- SAE reporting and follow up must be performed per protocol

### Protocol section 7.2 Important Medical Procedures to be Followed

### 7.2.3 Protocol Deviations

It is expected that more deviations than usual will be reported. Deviations related to the COVID-19 pandemic must be documented as such (COVID included in the deviation description). All deviations to the full protocol must be documented; local requirements for reporting of deviations covered by this addendum should be followed.

ADDENDUM VERSION 1.0

CONFIDENTIAL

PAGE 4

3.0 Scope

The SAP outlines the following:

- Study Objectives
- Study Design
- Study Endpoints
- Applicable Study Definitions
- Statistical Methods for analysis of all endpoints

4.0 Introduction

This SAP describes the statistical methods to be used during the reporting and analyses of data collected under Kymab Ltd Protocol KY1044-C01. It should be read in conjunction with the current study protocol and case report form (CRF). This version of the plan has been developed using protocol version 7.0 dated 18-Nov-2021 and CRF version 4.1 dated 06-Jul-2021. Any changes to the protocol or CRF may necessitate updates to the SAP.

Changes following approval of the first version of the SAP will be tracked in the Document History section of this document and a final version of the updated SAP will be approved prior to database lock.

5.0 Study Objectives

5.1 Primary Objectives

Phase 1:

To characterize the safety and tolerability of KY1044 as single agent and in combination with atezolizumab and to identify recommended doses for future studies.

Phase 2:

To estimate the anti-tumor efficacy of KY1044 as single agent and in combination with atezolizumab.

5.2 Secondary Objectives

- To evaluate the preliminary anti-tumor activity of KY1044 as single agent and in combination with atezolizumab (Phase 1 only).
- To characterize the safety and tolerability of KY1044 as single agent and in combination with atezolizumab (Phase 2 only).
- To characterize the pharmacokinetic (PK) profile of KY1044 as single agent and in combination with atezolizumab.
- To assess emergence of anti-KY1044 and anti-atezolizumab antibodies following one or more intravenous (i.v). infusions of KY1044 as single agent and/or in combination with atezolizumab, respectively.
- To assess changes in biomarkers from baseline in tumor tissue as potential predictors of efficacy of KY1044 as single agent and in combination with atezolizumab.
- To describe the survival rate at 12 and 24 months of patients treated with KY1044 as single agent and in combination with atezolizumab for each disease group.

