# Property of the Sanofi Group - strictly confidential

# 2.1.2 Secondary Objectives

- To evaluate the preliminary anti-tumor activity of KY1044 as single agent and in combination with atezolizumab (Phase 1 only)
- To characterize the safety and tolerability of KY1044 as single agent and in combination with atezolizumab (Phase 2 only)
- To characterize the PK profile of KY1044 as single agent and in combination with atezolizumab
- To assess PK of atezolizumab in combination with KY1044
- To assess emergence of anti-KY1044 and anti-atezolizumab antibodies following one or more IV infusions of KY1044 single agent and/or in combination with atezolizumab
- To assess changes in biomarkers from baseline in tumor tissue as potential predictors of efficacy of KY1044 as single agent and in combination with atezolizumab
- To describe the survival rate at 12 and 24 months of patients treated with KY1044 as single agent and in combination with atezolizumab for each disease group

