#### PK measures:

• Serum concentrations and PK parameters (eg, Cmax, t1/2) of KY1044 and of atezolizumab if in combination

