#### 6.4.2 Pharmacokinetic and Anti-drug Antibody Sampling Schedule

Serum concentrations of KY1044 and atezolizumab and detection of ADA will be assessed from blood samples taken during the study using validated bioanalytical methods. Assay methodologies and procedures will be described in analytical plans to be finalized before the start of sample analysis.

Multiple samples for concentration-time profiles for KY1044 will be taken in Cycles 1, 3 and 6 (see Table 6-5, Table 6-6, Table 6-7). For other cycles, samples will be taken for KY1044 serum concentrations and for atezolizumab serum concentrations at each cycle pre-infusion, end of infusion, End of Treatment and End of Study.

Anti-Drug Antibody samples will be drawn pre-infusion at all cycles and at the End of Study.

Samples will be collected at the timepoints specified in Table 6-5, Table 6-6, Table 6-7. Tolerances for deviation from the nominal time of sampling are provided in the tables below. These tolerances indicate the best time to allow interpretation of data. However, samples taken outside these tolerances will be evaluated so should be taken. The exact date and time of sampling will be recorded. Samples may also be drawn for serum concentration and/or ADA, with prior agreement with the Sponsor, at unscheduled times. Additionally, these blood samples may be used for *ad hoc* biomarker analysis (ie, safety and efficacy analyses).

Cycle	Day relative to most recent infusion	Scheduled timepoint and tolerance
Phase 1		
1	1	Pre-infusion of Cycle 1
1	1	End of KY1044 infusion (up to 5 min delay allowed) a
		1.5 h post-infusion start (±5 min) a
		2.5 h post-infusion start (±5 min) a
		8 h post-infusion start (±1 h) a
1	2	24 h post-infusion start (±2 h)
1	8	168 h post-infusion start (±8 h)
1	11	240 h post-infusion start (±24 h)
1	15	336 h post- infusion start (±24 h)
2	1	Pre-infusion of Cycle 2 (up to 24 h before 2 nd infusion)
		End of KY1044 infusion (up to 5 min delay) a
3	1	Pre-infusion of Cycle 3 (up to 24 h before 3 rd infusion)
		End of KY1044 infusion (up to 5 min delay) a
		1.5 h post-KY1044 infusion start (±5 min) a
3	8	168 h post-KY1044 infusion start (±8 h)
3	11	240 h post-KY1044 infusion start (±24 h)
3	15	336 h post-KY1044 infusion start (±24 h)
4	1	Pre-infusion of Cycle 4 (up to 24 h before 4 th infusion)
		End of KY1044 infusion (up to 5 min delay) a

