#### 9.4.4 Pharmacokinetic Analysis

The serum PK of KY1044 as a single agent, in combination with atezolizumab and for atezolizumab alone will be characterized using no compartmental analysis. The following PK measures will be calculated, whenever possible, from serum concentrations:

- Cmax: Maximum concentration (for atezolizumab only one timepoint of serum concentration at the end of infusion)
- tmax: Time of the maximum concentration (obtained without interpolation)
- Cmin: Trough concentrations
- $\lambda z$ : Terminal elimination rate constant (whenever possible)
- AUC0-last: Area under the concentration-time curve calculated using
- Linear trapezoidal summation from time 0 to time last, where "last" is the time of
- The last measurable concentration
- AUC0-inf: Area under the concentration-time curve from 0 to infinity,
- Calculated using the formula:  $AUC_{0-inf} = AUC_{0-last} + C_{last} / \lambda z$ , where  $\lambda z$  is the apparent terminal elimination rate constant
- Clearance
- Volumes of distribution
- t1/2: Half-life

For both KY1044 and atezolizumab, all peak (end-of-infusion) and trough (pre-infusion) concentrations will be tabulated. For KY1044 peak and trough concentrations will be tabulated separately for use as a single agent and for combination with atezolizumab.

Besides listings of pharmacokinetic measures for individual patients, all measures will be summarized. The summaries will include estimates of not only central tendency but variability such as Standard Error. For concentrations, geomeans will be provided. For  $t_{max}$  median (and range) and for half-lives, arithmetic means will be provided. Besides listings of concentrations, noncompartmental analysis (NCA) tables, charts illustrating the concentration-time profiles will be generated.

Additional pharmacokinetic analyses may be undertaken. For instance, if the tables of peak and trough concentration (or anti-drug antibody) indicate some kind of interaction between KY1044 and atezolizumab, pharmacokinetic modelling of these data may be undertaken. Exploratory analyses may also be conducted to estimate dose proportionality and accumulation ratio on relevant parameters.

Population PK analysis may be performed if deemed relevant and applicable, and the results will be summarized in a stand-alone report if deemed relevant. In this context, further exposure-response analyses may also be conducted.

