7.2.6 Pharmacokinetic Evaluable Set

The PK evaluable set will consist of all patients who had sufficient concentration-time data within the relevant phase to permit calculation of PK parameters for KY1044. For patients who were noncompliant with respect to administration of KY1044, or for patients with incomplete data, a decision as to their inclusion in the PK analysis will be made on a case-by-case basis. The PK evaluable set will be used for evaluation of PK parameters.

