10.6 Pharmacokinetic and Anti-drug Antibody Analyses

10.6.1 Pharmacokinetic Analyses

The serum PK of KY1044 as a single agent and in combination with atezolizumab will be characterized using non-compartmental analysis (NCA). Nominal times of sample collections will be used for the noncompartmental analysis (NCA). All BLQ values will be set to 0 units.

The following PK measures will be calculated, whenever possible, from serum concentrations:

C_{max}: Maximum concentration (for atezolizumab – only one time point of serum concentration at the end of infusion)

t_{max}: Time of the maximum concentration (obtained without interpolation)

Ctrough: Trough concentrations

 λ_z : Terminal elimination rate constant (whenever possible) using Linear Up Log Down method of determination and Best Fit setting.

AUC_{0-last}: Area under the concentration-time curve calculated using linear trapezoidal summation from time 0 to time last, where "last" is the time of the last measurable concentration

AUC_{0-inf}: Area under the concentration-time curve from 0 to infinity, calculated using the formula: AUC_{0-inf} = AUC_{0-last} + C_{last}/ λ_z , where λ_z is the apparent terminal elimination rate constant

Clearance

Volumes of distribution

t1/2: Half-life

The following diagnostic criteria will be used to flag individual data in Listings:

- %AUCextrap is 30% (criteria for exclusion of parameters: AUCinf, t-half, CL, CLss, Vz, Vss)
- Rsq < 0.7
- half-life calculated over a period of < 2 times the resultant half-life (Span)

For KY1044, all peak (end-of-infusion) and trough (pre-infusion) concentrations will be tabulated. For KY1044 peak and trough concentrations will be tabulated separately for use as a single agent and for combination with atezolizumab.

Besides listings of pharmacokinetic measures for individual patients, all measures will be summarized by descriptive statistics (N, Mean, SD, SE, Min, Median, Max, CV%, and Geometric Mean (only for ratios). The summaries will include estimates of not only central tendency but variability such as Standard Error (SE). For t_{max} median (and range) and for half-lives, arithmetic means will be provided. Besides listings of concentrations, NCA Mean parameter tables, charts illustrating the mean concentration-time profiles will be generated.

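### The SAP omits protocol 7.0's atezolizumab PK objective and, apart from an end-of-infusion Cmax remark, plans PK analysis for KY1044 only

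*SAP*

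**What the plan says.** **Protocol.** Section 2.1.2 lists atezolizumab PK as a secondary objective of its own: "To assess PK of atezolizumab in combination with KY1044". The matching endpoint in 2.2.2 is "Serum concentrations and PK parameters (eg, Cmax, t1/2) of KY1044 and of atezolizumab if in combination". Sampling follows from this. Under 6.4.2, outside the intensive KY1044 cycles, "samples will be taken for KY1044 serum concentrations and for atezolizumab serum concentrations at each cycle pre-infusion, end of infusion", and Table 6-6 sets atezolizumab samples in every cycle for combination patients. Section 9.4.4 then gives the analysis: "The serum PK of KY1044 as a single agent, in combination with atezolizumab and for atezolizumab alone will be characterized using no compartmental analysis", and "For both KY1044 and atezolizumab, all peak (end-of-infusion) and trough (pre-infusion) concentrations will be tabulated".

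**SAP.** Section 4.0 states that this version was developed from protocol version 7.0. Section 5.2 has one PK objective, "To characterize the pharmacokinetic (PK) profile of KY1044 as single agent and in combination with atezolizumab", and none for atezolizumab. The PK evaluable set in 7.2.6 requires "sufficient concentration-time data within the relevant phase to permit calculation of PK parameters for KY1044". The table commitment in 10.6.1 is "For KY1044, all peak (end-of-infusion) and trough (pre-infusion) concentrations will be tabulated". Atezolizumab concentrations appear once in 10.6.1, in the Cmax definition, where a parenthesis notes that the drug has a single time point at the end of infusion.

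SAP section numbers here are those printed in the body. The SAP's table of contents and internal cross-references use a different numbering.

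**The concern.** The quoted SAP objective is correct in itself, since it matches a protocol objective. The defect is that the next protocol objective is missing and that the rest of the SAP's PK text has narrowed in the same direction. Protocol 9.4 leaves the full analysis details to the SAP, so a programmer working from the SAP would produce KY1044 tables and stop there.

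Two things are at stake. A secondary objective of the current protocol would reach the study report with little or nothing behind it. The atezolizumab half of the peak and trough tables, which protocol 9.4.4 names as one place to look for an interaction between the two drugs, would also be missing. Those tables are where an effect of KY1044 on atezolizumab exposure would show, if there is one.

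**Working it through.** The point rests on no sample size, power or event count, so the check is a comparison of the two documents.

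| Element | Protocol 7.0 | SAP |
|---|---|---|
| Secondary objectives | Seven in 2.1.2, including atezolizumab PK | Six in 5.2; the missing one is atezolizumab PK |
| PK endpoint | Both drugs (2.2.2) | KY1044 only (7.1 and 10.5.3) |
| PK analysis set | Left to the SAP (9.3.2) | Defined by KY1044 parameters only (7.2.6) |
| Non-compartmental analysis | KY1044 alone, KY1044 in combination, and atezolizumab (9.4.4) | KY1044 alone and in combination (10.6.1) |
| Peak and trough tables | Both drugs (9.4.4) | KY1044 only (10.6.1) |
| Cmax definition | Mentions atezolizumab, end of infusion | Same mention kept |

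**Is this text that lagged behind an amendment?** The amendment summary at the front of protocol 7.0 records that this version added the atezolizumab objective and replaced a KY1044-only endpoint with the two-drug one. SAP 7.1 and 10.5.3 still carry KY1044-only endpoint wording. SAP 4.0 nevertheless cites version 7.0 as its basis. It gives a date of 18-Nov-2021 where the protocol is dated 10 November 2021, but the version number is clear. The SAP's document history for version 3.0 says only that PK section 10.6.1 was updated and gives no reason for narrowing its scope.

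**How much of the data is left out?** Table 6-6 schedules, for a combination patient treated for n cycles:

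- n pre-infusion samples (the first is a baseline, the other n − 1 are troughs);
- n end-of-infusion samples;
- 1 at end of treatment and 1 at the end of safety follow-up.

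The total is n + n + 1 + 1 = 2n + 2. The surviving Cmax remark covers at most the n end-of-infusion samples, so n + 2 have no planned summary. For n = 6, chosen as an illustration, the total is 2 × 6 + 2 = 14, of which 6 are covered and 6 + 2 = 8 are not (8/14 = 57%).

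**Could the existing PK set serve?** A combination patient with atezolizumab concentrations but too few KY1044 data to derive KY1044 parameters does not meet the criterion in 7.2.6. Inclusion of patients with incomplete data is then decided case by case. The set is therefore not defined for atezolizumab.

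**The case against.** The best defence has four parts.

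1. **Some analysis survives.** SAP 10.6.1 lists Cmax with its atezolizumab remark and then says all measures will be summarised. Other entries in that list, including trough, name no drug, so a generous reader could extend them to atezolizumab. SAP 4.0 also says the SAP is to be read with the protocol, and protocol 9.4.4 still requires the tables. This stands in part. A reader might infer that atezolizumab PK has no analysis at all, and the documents do not support that. But the sentence introducing the list, the evaluable set and the tabulation sentence all name KY1044 only. Reading the two documents together leaves open whether the atezolizumab tables are required or were dropped on purpose.

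2. **The samples may be used elsewhere.** A reader might infer that the atezolizumab samples go unused. The end-of-infusion values feed the retained Cmax. Protocol 9.4.4 allows population PK and exposure-response work, and 6.4.2 allows ad hoc biomarker use. These uses are optional and do not replace the planned tables, but they rule out saying the samples are wasted.

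3. **The prompt for interaction modelling is not gone.** Protocol 9.4.4 offers modelling as an optional example, prompted by peak and trough tables or by anti-drug antibody data. The SAP keeps KY1044 tables split by single agent and combination (10.6.1) and antibody summaries for both drugs (10.6.2). Only the atezolizumab concentration part is lost.

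4. **The design limits the answer anyway.** A reader might infer that this omission is what prevents the trial from saying whether KY1044 alters atezolizumab exposure. Every planned combination dose level in protocol Table 5-3 pairs atezolizumab with KY1044, and under protocol section 8 patients who stop KY1044 for adverse events also stop atezolizumab. There is no internal comparator without KY1044. Restored tables could show at most a trend across KY1044 dose levels (0.8 to 240 mg in Table 5-3), or be set beside external data.

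All four narrow the consequence. None explains the missing objective, endpoint, analysis set and tables.

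**Conclusion.** The omission is confirmed. The SAP claims protocol 7.0 as its basis, leaves out one of that version's seven secondary objectives, and restricts the endpoint, PK set, non-compartmental analysis and peak/trough tables to KY1044. The end-of-infusion Cmax remark is not enough to answer the objective, so atezolizumab PK has no adequate prespecified analysis. Taken literally, the SAP leaves atezolizumab trough, end-of-treatment and follow-up concentrations untabulated and drops the atezolizumab half of the tables used to look for an interaction.

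The size is moderate. The objective is descriptive, sampling is sparse, and no primary endpoint in either phase is touched. The change should be made but does not threaten the trial's main conclusions. The verdict assumes that no separate PK analysis plan, unmentioned in the two documents, covers atezolizumab. If one exists, the SAP should refer to it.

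**What to change.** Before database lock:

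- **SAP 5.2:** add the atezolizumab PK objective from protocol 2.1.2.
- **SAP 7.1 and 10.5.3:** replace the KY1044-only PK endpoint with the protocol's two-drug endpoint.
- **SAP 7.2.6:** add an atezolizumab PK set, for example combination patients with at least one post-dose atezolizumab concentration. The protocol does not prescribe this definition, so another workable one would do.
- **SAP 10.6.1:** restore atezolizumab to the non-compartmental analysis sentence and the peak/trough tables. Tabulate by cycle and KY1044 dose level, and include the end-of-treatment and follow-up concentrations. The breakdown by dose level is a suggestion, made because a trend across doses is the only comparison within the trial. State which atezolizumab parameters will be derived; with pre-infusion and end-of-infusion samples plus two late ones, little beyond peak and trough may be estimable.

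If the narrowing was deliberate, the SAP should instead say so, justify the departure from protocol 9.4.4 and log it in the document history.

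The cost is SAP wording and a few tables. The samples are already in the protocol's schedule, so no new data collection is needed.
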